## 671 **6.2 Statistical analysis plan**

### 672 *6.2.1 General considerations*

673 The statistical analyses and reporting will adhere to the CONSORT guidelines. All tests will be  
674 two-sided, a p-value < 0.05 will be considered significant, and all confidence intervals will have 95%  
675 coverage. All analyses will be conducted on a modified intention-to-treat basis only including  
676 participants receiving at least the first dose of the study medications. In a double-blind trial, this  
677 approach is unbiased while increasing precision. The two groups will be compared in relation to  
678 baseline characteristics using descriptive statistics.

679

680 The persons conducting the statistical analysis will be blinded to the randomized allocation. Groups  
681 will be designated as “A” and “B” until all pre-specified analyses are performed and shared with all  
682 authors and the Data Safety Monitoring Board.

683

### 684 *6.2.2 SOFA score and renal failure*

685 The change in SOFA score will be calculated and compared between groups using the Wilcoxon  
686 Rank Sum test (if the change is not normally distributed) or by a t-test if the change is approximately  
687 normally distributed. Fisher’s exact tests will be used to compare the incidence of renal failure  
688 during the index ICU stay.

689

690 If a participant expires prior to the 72-hour time point, SOFA scores will be imputed based on a pre-  
691 defined plan as follows. If a participant expires before 24-hours has elapsed, a 20% increase from  
692 baseline will be imputed. If a participant expires between 24-hours and 48-hours, a 15% increase  
693 from the 24-hour time point will be imputed. If a participant dies between 48-hours and 72-hours, a  
694 20% increase from the 24-hour time point will be imputed. Sensitivity analyses will be performed  
695 using various other imputation techniques. Specifically, we will perform 1) a sensitivity analysis in  
696 which the worst possible SOFA score (score of 24) is imputed for those participants who expire, 2) a  
697 sensitivity analysis in which the last SOFA score for participants who expire will be carried forward,  
698 and 3) a sensitivity analysis in which only those patients who survive to 72-hours are included.  
699 These sensitivity analyses were chosen to model ‘worst-possible’ and ‘best-possible’ scenarios. For  
700 the secondary outcome of renal failure, participants who expire during their ICU stay will be  
701 assessed to have developed renal failure if they demonstrated any degree of unresolved KDIGO  
702 acute kidney injury prior to death. If there was no evidence of acute kidney injury prior to death or if  
703 kidney injury had fully resolved, these participants will be assessed as not having developed renal  
704 failure.

705

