## 6. SAMPLE SIZE CALCULATION AND STATISTICAL ANALYSIS PLAN

### 6.1 Sample size calculation

The study has been powered to have at least 80% power for the primary outcome and all key secondary outcomes as follows:

**SOFA Score:** Based on preliminary data, we conservatively anticipate a decrease in SOFA score of 6 (standard deviation [SD]: 4) in the treatment group and 4 (SD: 2) in the placebo group. With these estimates, enrollment of **200 participants (100/arm)** at an alpha of 0.05 and using a t-test with unequal variance, the trial will provide > 99% power to detect a statistical significant difference between groups.

**Kidney Injury:** Based on preliminary data from our study of vitamin B1 in septic shock, we anticipate that 30% of participants in the treatment group and 55% in the placebo group will have renal failure which will result in a 94% power for this outcome. This calculation and following calculation were performed using the Fisher's exact test.

**Mortality:** Based on preliminary data, we anticipate that the control group will have a mortality of 40%. We estimate a treatment effect of 50% (risk ratio: 0.50) resulting in a mortality of 20% in the treatment group. With these estimates, 182 participants will lead to 80% power. To further increase

the trial's power and due to potential loss-to-follow-up, we will aim to enroll 200 participants. These estimates are conservative compared to the Marik et al. study which found a treatment effect corresponding to a risk ratio of 0.21 which persisted in adjusted analysis.

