## 6.2 Statistical analysis plan

### 6.2.1 General considerations

The statistical analyses and reporting will adhere to the CONSORT guidelines. All tests will be two-sided, a p-value  $< 0.05$  will be considered significant, and all confidence intervals will have 95% coverage. All analyses will be conducted on a modified intention-to-treat basis only including participants receiving at least the first dose of the study medications. In a double-blind trial, this approach is unbiased while increasing precision. The two groups will be compared in relation to baseline characteristics using descriptive statistics.

The persons conducting the statistical analysis will be blinded to the randomized allocation. Groups will be designated as "A" and "B" until all pre-specified analyses are performed and shared with all authors and the Data Safety Monitoring Board.

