### 6.2.2 SOFA score and renal failure

The change in SOFA score will be calculated and compared between groups using the Wilcoxon Rank Sum test (if the change is not normally distributed) or by a t-test if the change is approximately normally distributed. Fisher's exact tests will be used to compare the incidence of renal failure during the index ICU stay.

If a participant expires prior to the 72-hour time point, SOFA scores will be imputed based on a pre-defined plan as follows. If a participant expires before 24-hours has elapsed, a 20% increase from baseline will be imputed. If a participant expires between 24-hours and 48-hours, a 15% increase from the 24-hour time point will be imputed. If a participant dies between 48-hours and 72-hours, a 20% increase from the 24-hour time point will be imputed. Sensitivity analyses will be performed using various other imputation techniques. Specifically, we will perform 1) a sensitivity analysis in which the worst possible SOFA score (score of 24) is imputed for those participants who expire, 2) a sensitivity analysis in which the last SOFA score for participants who expire will be carried forward, and 3) a sensitivity analysis in which only those patients who survive to 72-hours are included. These sensitivity analyses were chosen to model 'worst-possible' and 'best-possible' scenarios. For the secondary outcome of renal failure, participants who expire during their ICU stay will be assessed to have developed renal failure if they demonstrated any degree of unresolved KDIGO acute kidney injury prior to death. If there was no evidence of acute kidney injury prior to death or if kidney injury had fully resolved, these participants will be assessed as not having developed renal failure.

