### 413 **4.4 Drug preparation and administration**

414 The vitamin C and vitamin B1 will be mixed together in 100ml of normal saline and administered  
415 intravenously over 45-60 minutes. The hydrocortisone will be given intravenously as a push-dose in  
416 1ml of saline over 1-2 minutes. The placebo will be given using techniques and volumes matching  
417 those of the study medications.

418  
419 All study medications will be continued for 4-days or until the participant expires or leaves the  
420 intensive care unit.

421  
422 **4.4.1 Contingencies and Participant Withdrawal**

- 423 • In the unlikely event that a participant is discharged alive from the hospital prior to 4 days after  
424 enrollment, all study medications will be stopped. The participant will remain in the study and will  
425 be followed for outcomes.
- 426 • Hydrocortisone is occasionally used for refractory septic shock. If the clinical team opts to provide a  
427 participant hydrocortisone, the hydrocortisone will be given open-label but the vitamin C/B1 will  
428 remain randomized and blinded. In this case, the research team will ensure that study  
429 hydrocortisone/placebo is replaced by open-label hydrocortisone. The participant will remain in  
430 the study and will be followed for outcomes.
- 431 • If the clinical team decides to give the participant vitamin B1 for clinical purposes, the study drug  
432 will be continued (including thiamine) as long as the total maximum dose of vitamin B1 is  
433  $\leq 1,500\text{mg/day}$ . 1,500mg day is a standard dose for Wernicke's encephalopathy at many  
434 institutions and has not been associated with any increased harm.
- 435 • If the clinical team decides to give the participant vitamin C for clinical purposes, further  
436 administration of study meds will be stopped. The participant will remain in the study and will be  
437 followed for outcomes.
- 438 • If a participant withdraws from the study, further administration of study meds will be stopped.  
439 Data collected prior to withdrawal will be maintained but additional data will not be collected.

440  
441 **4.5 Specimen collection procedures**

442 **4.5.1 Timing and volume of blood draw**

443 All participants will have a blood samples collected at four time-points and urine samples at two  
444 time-points (if not already available as part of routine clinical care). Blood will be obtained by  

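### The SOFA sensitivity analyses vary only the handling of early deaths, alike in both arms, so they do not bound the treatment effect, and no rule covers survivors without a 72-hour score

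*SAP*

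**What the plan says.** Protocol 6.2.2 and SAP 6.2.2 carry the same text. Change in SOFA is compared by a t-test or, if not normally distributed, by the Wilcoxon rank sum test. The main analysis raises the score of a participant who dies before 72 hours: by 20% of baseline (death before 24 hours), 15% of the 24-hour score (24 to 48 hours) or 20% of the 24-hour score (48 to 72 hours). Three sensitivity analyses follow: one in "which the worst possible SOFA score (score of 24) is imputed for those participants who expire", one carrying the last score forward, and "a sensitivity analysis in which only those patients who survive to 72-hours are included". The section then says: "These sensitivity analyses were chosen to model" worst-possible and best-possible scenarios. It does not say which analysis is which, or what is worst or best: the patient's score or the treatment effect.

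On who is analysed, 6.2.1 says: "All analyses will be conducted on a modified intention-to-treat basis only including" those given at least a first dose. On withdrawal, 4.4.1 says: "Data collected prior to withdrawal will be maintained but additional data will not be collected". Section 6.2.2 gives no rule for a participant alive at 72 hours whose score is missing, and no arm-specific or tipping-point analysis is planned.

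**The concern.** A sensitivity set described as running from worst to best invites the reader to treat its ends as limits on the treatment effect. These cannot be limits. Analyses 1 and 2 give deaths a different value by one rule for both arms, and analysis 3 removes deaths from both arms, which conditions on a post-randomisation outcome. None takes an assumption unfavourable to one arm only.

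The scores that are actually unknown are also never tested. A participant who withdraws, leaves hospital before 72 hours, or lacks one SOFA component has no change score, so a two-sample test on change leaves that person out. Early deaths stay in with worsened scores. If live missing scores are unequal between arms or related to recovery, the primary comparison shifts and no planned analysis would show it.

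**Working it through.** **Inputs from the documents.** Protocol 6.1: "anticipate a decrease in SOFA score of 6 (standard deviation [SD]: 4) in the treatment group and 4 (SD: 2) in the placebo group", 100 per arm; 30-day mortality 20% on treatment and 40% on placebo. Protocol 6.2.1: "All tests will be two-sided". SOFA has six components scored to 4, so its maximum is 24.

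**Assumptions (not in the documents).** Early deaths are a quarter to a half of the planned 30-day deaths: 5% v 10% up to 10% v 20% (treatment v placebo). Baseline SOFA is 9, the subgroup cut-off. The last score before death equals baseline. The SD is 3 per arm where survivors are taken as equal. Live missing scores are 2% to 10% per arm.

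**The plan's own figure.** SE = √(16/100 + 4/100) = 0.447, noncentrality 2/0.447 = 4.47, Welch df about 146, power 99.35%. This agrees with the statement "at an alpha of 0.05 and using a t-test with unequal variance, the trial will provide > 99% power".

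**Deaths.** Let dT and dC be the early-death proportions, μT and μC the survivor changes, and v the change assigned to a death. Positive D favours the regimen:

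D(v) = [(1−dC)μC + dC·v] − [(1−dT)μT + dT·v]

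Main rule: v = 0.2 × 9 = 1.8. Score 24: v = 24 − 9 = 15. Carried forward: v = 0. Survivors only: D = μC − μT. Raising a common v by x moves D by (dC − dT)·x.

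Example, 5% v 10%, score 24: placebo 0.9(−4) + 0.1(15) = −2.10; treatment 0.95(−6) + 0.05(15) = −4.95; D = 2.85.

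The arm-specific column scores treated deaths 24 with placebo deaths carried forward, then the reverse.

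| Early deaths, T v C | Survivor change, T v C | Main | Score 24 | Carried forward | Survivors | Arm-specific |
|---|---|---|---|---|---|---|
| 5% v 10% | −6 v −4 | 2.19 | 2.85 | 2.10 | 2.00 | 1.35 to 3.60 |
| 10% v 20% | −6 v −4 | 2.38 | 3.70 | 2.20 | 2.00 | 0.70 to 5.20 |
| 10% v 10% | −6 v −4 | 1.80 | 1.80 | 1.80 | 2.00 | 0.30 to 3.30 |
| 10% v 5% | −6 v −4 | 1.51 | 0.85 | 1.60 | 2.00 | 0.10 to 2.35 |
| 5% v 10% | −4 v −4 | 0.29 | 0.95 | 0.20 | 0.00 | −0.55 to 1.70 |

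Score 24 exceeds survivors-only when 19·dC > 21·dT, a placebo-to-treatment death ratio above 21/19 = 1.11.

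**Test scale.** Score 24 also widens the SE. At 5% v 10% with the planned changes, the SE is 0.85 and z = 2.85/0.85 = 3.35, against 4.40 (main), 4.48 (carried forward) and 4.33 (survivors). In 3,000 simulated trials, Welch power was 76% for score 24 against 92%, 93% and 90%; Wilcoxon power was 96% against 95%, 95% and 93%. (The simulation used whole-number scores kept within 0 to 24, which shrinks the survivor difference to about 1.3.)

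**Live participants without a 72-hour score.** With fraction m missing per arm and difference δ among them, D = 2(1−m) + mδ.

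- Quartile version: planned best-quartile falls are 4 + 0.6745×2 = 5.349 (placebo) and 6 + 0.6745×4 = 8.698 (treatment). Unfavourable: treated missing unchanged, placebo missing fall 5.349, so D = 2 − 7.349m. Favourable: the reverse, D = 2 + 6.698m.
- Wider version: falls of 8 (placebo) and 10 (treatment), so D = 2 − 10m and 2 + 8m.

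| m | Quartile bounds | Wider bounds |
|---|---|---|
| 2% | 1.85 to 2.13 | 1.80 to 2.16 |
| 5% | 1.63 to 2.33 | 1.50 to 2.40 |
| 10% | 1.27 to 2.67 | 1.00 to 2.80 |

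**Scale maximum.** 1.2 × 21 = 25.2 and 1.15 × 21 = 24.15, both above 24. With baseline normal, mean 10 and SD 3, a whole-number score of 21 or more has probability P(Z > (20.5 − 10)/3 = 3.5), about 0.02%.

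**The case against.** The plan's phrase about the worst possible value describes a patient's score, and nothing in 6.2.2 claims limits on the treatment effect. That stands: the fault is an undefined label that can be misread, not a numerical error.

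A reader might infer that the score-24 analysis is in general the one most favourable to the regimen. The documents do not support that. It holds for the mean difference when early deaths clearly fall on treatment. Under the planned effect, score 24 gives the lowest Welch z and about the same Wilcoxon power as the main rule, and Wilcoxon is what the plan specifies for non-normal changes. With equal survivors at 5% v 10%, Welch rejects in 21% of simulated trials for score 24 against 11% for the main rule, but Wilcoxon in 9% for both. Nor would such a rejection be spurious: early mortality is halved in that scenario, which is a real benefit.

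A reader might also infer that survivors-only is the most conservative analysis whenever treatment has fewer early deaths. At 10% v 12% with baseline 10 and the planned changes, carried forward gives 0.88(−4) − 0.90(−6) = 1.88, below survivors-only at 2.00; score 24 gives 2.16.

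On live missing scores, 4.4.1 calls hospital discharge before day 4 unlikely and keeps such participants in follow-up, and day 4 falls after 72 hours. Section 6.2.1 defines who is analysed, not that each has a score. So the number affected may be small and is unknown. None of this supplies a rule for them. The survivors-only analysis and the Kaplan-Meier curves by arm do help the reader separate mortality from organ function, and the excess over 24 will be rare.

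**Conclusion.** The point holds in a limited form. The three analyses vary only how deaths before 72 hours are handled, identically in both arms, and do not bound the treatment effect. In the first row of the table the main rule and the three analyses span 0.85 points, against 2.25 for arm-specific extremes. With equal survivors at 5% v 10% they never go below zero, while the arm-specific extremes reach −0.55.

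The practical gap is the living participant without a 72-hour SOFA, who drops out of the primary comparison and every sensitivity analysis. Under the planned effect even 10% missing per arm leaves the bounds above zero, so this is a cheap improvement rather than a threat to the design; a smaller true effect would have less room. The missing cap is certain arithmetic with little expected effect. The sizes rest on assumed early-death rates, baseline SOFA and missingness; the structural points do not.

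**What to change.** In 6.2.2, before unblinding:

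1. Keep dosed, living participants without a 72-hour SOFA in the primary analysis by multiple imputation from baseline, 24-hour and any other SOFA components actually recorded. Section 4.5.2 specifies only laboratory tests at 120 hours, so the other components cannot be assumed available then. State how results are pooled if the Wilcoxon test is used.
2. Add an arm-specific or tipping-point analysis for these scores and, separately, for deaths. State the imputed values in advance and make any quoted bounds match them. For deaths, one pair is treated deaths at 24 with placebo deaths carried forward, and the reverse.
3. Cap every imputed score at 24.
4. State that worst and best refer to the score given to deaths, not to bounds on the treatment effect, and report deaths before 72 hours by arm beside the SOFA results.

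The cost is SAP text, modest programming and a wider sensitivity range to report. Multiple imputation is already planned for the SF-36 in 6.2.4, so the method is not new to the plan. The case report form should be checked for which components are held at each time point.

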### 706 *6.2.3 30-day mortality*

707 Survival until 30 days will be analyzed using survival analysis. Participants lost to follow-up will be  
708 censored and the censoring will be assumed non-informative. Results will be presented with  
709 Kaplan-Meier curves and the groups compared using the log-rank test. Hazard ratios with 95%  
710 confidence intervals will be obtained using Cox’s proportional hazards models. The proportional  
711 hazards assumption will be verified by visual inspection of the Kaplan-Meier curves and statistically  
712 by including a product term (i.e. “interaction”) between the treatment group variable and the natural  
713 logarithm of time in the model. If the proportional hazards assumption is not met, only the Kaplan-  
714 Meier curves and the p-value from the log-rank test will be presented.

715

716 Adverse events and other binary outcomes will be presented and analyzed like renal failure.

717

### 718 *6.2.4 Additional Secondary Analyses*

719 Both ICU and hospital length of stay will be compared using Wilcoxon Rank Sum tests. Ventilator  
720 and shock free days over the first 7-days after enrollment will likewise be compared using the

721 Wilcoxon Rank Sum given that the data will likely be not normally distributed. In these latter two  
722 analyses, patients who expire prior to 7-days will be assessed to have 0 ventilator or shock free  
723 days if they had died while on a ventilator or vasopressor respectively. The incidence of delirium will  
724 be compared using the Fisher's exact test. For the quality-of-life outcome (i.e. 90-day SF-36), the  
725 primary analysis will only include patients with available data. As a secondary analysis, multiple  
726 imputation will be used to estimate SF-36 scores in all patients not known to be dead at 90 -days.  
727

### 728 *6.2.5 Subgroup analyses*

729 The analysis will include three pre-defined subgroup analyses for the primary and key secondary  
730 outcomes according to 1) participants with initially high SOFA scores ( $\geq 9$ ). This cut-off was chosen  
731 to represent a population with a  $\geq 50\%$  predicted likelihood of mortality 2) baseline vitamin B1  
732 deficiency and 3) baseline adrenal insufficiency. We will not plan to perform a subgroup analysis  
733 according to vitamin C deficiency, as prior work has shown that the vast majority of participants with  
734 septic shock have vitamin C levels below the reference range. Vitamin B1 deficiency will be  
735 defined as a plasma vitamin B1 level  $\leq 7$  nmol/L as has been previously described. Adrenal  
736 insufficiency will be defined as a cortisol level  $< 10\mu\text{g/dL}$ . The trial is not powered to detect  
737 subgroup differences and these will be considered exploratory and hypothesis generating.  
738

### 739 *6.2.6 Statistical stopping criteria*

740 Since the primary outcome is not mortality, there will be no formal stopping criteria for efficacy.  
741 There will be no predefined stopping criteria for futility since enrollment of the full cohort might allow  
742 for detection of efficacy in subgroups or in other outcomes even if the primary outcome is negative.  
743

## 744 **7. DATA COLLECTION AND MANAGEMENT**

### 745 **7.1 Data collection process**

746 Data collection will be the responsibility of the individual site investigators with oversight from the trial  
747 coordinating center. Most variables (i.e. demographics, sepsis characteristics and laboratory  
748 results) will be obtained prospectively from the electronic medical record. 30-day follow-up  
749 regarding safety and mortality end-points will be obtained via telephone call post-discharge (unless  
750 the participant remains in the hospital at 30-days). Data will be entered directly into the online  
751 database software (see below).  
752

### 753 **7.2 Variables**

754 Will be provided on the online CRF. A PDF version is available upon request.  
755

### 756 **7.3 Data quality and validity**

757 Data quality and validity will be optimized by using a detailed data dictionary which will be  
758 distributed to all sites. Data quality will be monitored both centrally by the coordinating site and  
759 locally by each site principal investigator.  
760

### 761 **7.4 Data storage and security**

762 The database application we will use is REDCap Cloud (<https://www.redcapcloud.com/>). REDCap  
763 Cloud is a professional database that provides a user-friendly interface. The REDCap Cloud data  
764 management system is secure, fully compliant with all regulatory guidelines, and includes a  
765 complete audit-trail for data entry validation. Through these mechanisms, as well as relevant  
766 training for all involved parties, participant confidentiality will be safeguarded. All members of the  
767 research team will be required to complete standardized training in REDCap cloud, which will be  
768 documented within the software.  
769

770 The consent form and other trial documents for each participant will initially be stored in a secure,  
771 locked place at the individual sites. Participating sites will be responsible for maintaining their own  
772 trial documents and study materials (e.g. signed ICFs, site logs etc). Trial documents generated at  
773 the Coordinating Center will be maintained the Coordinating Center. Following completion of the

774 trial, documents will be maintained for a period of at least 2-years at each site per FDA regulations  
775 (or longer depending on local IRB guidelines).

776

